8.2.6. Progression-free Survival

Progression-free Survival (PFS) per RECIST 1.1 and Lugano is calculated from the date of first WTX-330 dose to the date of disease progression or death, whichever occurs first. The subjects without disease progression or death will be censored on the date of last disease assessment. See event/censoring rules in section 8.2.5.

Immuno Progression-free Survival (iPFS) per iRECIST, is calculated from the date of first WTX-330 dose to the date of first iUPD that is confirmed in subsequent assessments (iCPD), the date of first iUPD that is

QMS Document Name: Statistical Analysis Plan Template(EN)	Page 20 of 41
QMS No (include version ref): STF-015-GL.03	Document date: 14JUL2022
CONFIDENTIAL	

not followed any of iSD/iPR/iCR in subsequent assessments, or death, whichever occurs first. The subjects without iUPD/death, or with iUPD being annulled by subsequent assessments (iSD, iPR, iCR) will be censored at the date of last assessment.

Alive subjects without postbaseline assessment will be censored at the date of first WTX-330 dose (day 1).

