8.2.1. Individual Time Point Response

According to RECIST 1.1, the time point response will be evaluated as Complete Response (CR), Partial Response (PR), Stable Disease (SD), Progressive Disease (PD), Not Evaluable (NE). According to iRECIST, the time point response will be evaluated as Immune unconfirmed progressive disease (iUPD), Immune confirmed progressive disease (iCPD), Immune complete response (iCR), Immune partial response (iPR), Immune stable disease (iSD), Not Evaluable (NE). According to Lugano classification, the Lugano (Metabolic/PET-CT Based) time point response will be evaluated as Complete Response (CR), Partial Remission/Response (PR), Stable Disease (SD), and Progressive Disease (PD).

The following RECIST 1.1, iRECIST 1.1, and Lugano time point response(s) will be excluded from derivation of Best Overall Response (BOR), Clinical Benefit Rate (CBR), Duration of Response (DOR), Progression free Survival (PFS), Immuno Best Overall Response (iBOR), Immuno Clinical Benefit Rate (iCBR); Immuno Duration of Response (iDOR), Immuno Progression free Survival (iPFS):

- All RECIST 1.1, iRECIST 1.1 and Lugano time point response(s) after Antineoplastic therapy (including radiotherapy, surgery and medication) will be excluded
- For RECIST 1.1 and Lugano, any time point response(s) after the first PD will be excluded
- For iRECIST, any time point response(s) after the first iCPD will be excluded

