8.2.5. Duration of Response

Duration of response (DOR), reported the subjects achieving confirmed PR or CR per RECIST 1.1, is calculated from the date of first observation of CR or PR to the date of disease progression using RECIST 1.1 criteria or death, whichever occurs first. The subjects without disease progression or death will be censored on the date of last disease assessment. See below for event/censoring rules.

Situation	Date of Event or Censoring	Event or Censoring
** using the derived dataset as described in section 8.2.1		
Progression after one or none missing assessment	Date of progression	Event
Death after one or none missing assessment	Date of death	Event
No progression (or death)	Date of last assessment	Censored
Progression or death after two or more missing assessment	Date of last assessment prior to missed assessments	Censored

Duration of response (DOR), reported the subjects achieving CR or PR of BOR per Lugano, is calculated from the date of first observation of CR or PR to the date of disease progression using RECIST 1.1 criteria or death, whichever occurs first. The subjects without disease progression or death will be censored on the date of last disease assessment. See above for event/censoring rules.

Immuno Duration of response (iDOR), reported the subjects achieving iCR or iPR per iRECIST, is calculated from the date of first observation of iCR or iPR to the date of first iUPD that is confirmed in subsequent assessments (iCPD), the date of first iUPD that is not followed any of iSD/iPR/iCR in subsequent assessments, or death, whichever occurs first. The subjects without iUPD/death, or with iUPD being annulled by subsequent assessments (iSD, iPR, iCR) will be censored at the date of last assessment.

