8.3.5. Analysis of Time to Events

Time to event parameters (DoR, iDoR, PFS, iPFS, OS) will be estimated using the Kaplan-Meier method (Kaplan & Meier, 1958). The number and percentage of subjects with events/censored, the 1st quartile (25%), median, 3rd quartile (75%), and their 2-sided 95% confidence interval, event-free rate at 3/6/9/12/15 months and their 2-sided 95% confidence interval will be presented.

Event or censor category of each subject in the summary for DoR, iDoR, PFS, iPFS will be presented. Event categories include progression and death. Censor categories include No progression and death, Progression or death after antineoplastic therapy, Progression or death after two or more missing assessment.

Kaplan-Meier curves for PFS, iPFS and OS of expansion cohorts will be plotted.

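### For patients whose iUPD is annulled and who later progress or die, SAP 8.2.5 and 8.2.6 give two conflicting instructions: one sentence makes them events, and the next, taken literally, censors them

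*SAP*

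**What the plan says.** SAP 8.2.5 dates the iDOR event at "the date of first iUPD that is confirmed in subsequent assessments (iCPD), the date of first iUPD that is not followed any of iSD/iPR/iCR", or at death. SAP 8.2.6 uses the same construction for iPFS, and its event sentence ends "not followed any of iSD/iPR/iCR in subsequent assessments, or death, whichever occurs first". Neither section makes an exception for a patient who had an earlier iUPD that was annulled.

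In both sections the next sentence deals with censoring. In 8.2.5 it reads "The subjects without iUPD/death, or with iUPD being annulled by subsequent assessments (iSD, iPR, iCR) will be censored at the date of last assessment". In 8.2.6 it likewise says that subjects "with iUPD being annulled by subsequent assessments (iSD, iPR, iCR) will be censored at the date of last assessment".

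Two other sections bear on the point:

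- SAP 8.2.1 sets which assessments enter the derivation. Apart from those after antineoplastic therapy, "For iRECIST, any time point response(s) after the first iCPD will be excluded". Assessments after an annulled iUPD therefore stay in.
- SAP 8.3.5 states "Event or censor category of each subject in the summary for DoR, iDoR, PFS, iPFS will be presented" and adds "Event categories include progression and death". It names three censor categories: no progression or death, an event after antineoplastic therapy, and an event after two or more missing assessments.

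**The concern.** The censoring sentence names two groups joined by 'or'. The first, subjects with neither iUPD nor death, carries its own no-event condition. The second, subjects with an annulled iUPD, carries none. A patient whose iUPD is annulled and who later has a confirmed progression or dies therefore fits the event sentence and the censoring sentence at once.

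These are patients whom the immune criteria are designed to keep following, and SAP 8.2 continues scanning until iCPD, so their later events will usually be observed. If the censoring sentence is programmed as written, those events become censored records. PFS per iRECIST is a Part 2 secondary endpoint (SAP 1.2), and SAP 8.3.5 plans Kaplan-Meier estimates for iPFS and iDoR. Two programmers working from the same text could produce different estimates from the same data.

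**Working it through.** The plan states no figure for iPFS or iDOR, so there is none to reproduce. The check applies each sentence in turn to example timelines.

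**Inputs.** Scans fall every 8 weeks for the first 6 cycles and every 12 weeks after that (SAP 8.2). Six 28-day cycles are 24 weeks, so scans fall at weeks 8, 16, 24 and 36. Study day = 7 × week + 1, and a month is 30.4375 days (SAP Appendix 4). An expansion arm has up to 20 patients (SAP 3.2).

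**Dates.**

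- Week 8: day 57, 57 / 30.4375 = 1.9 months
- Week 16: day 113, 113 / 30.4375 = 3.7 months
- Week 22: day 155, 155 / 30.4375 = 5.1 months
- Week 24: day 169, 169 / 30.4375 = 5.6 months
- Week 36: day 253, 253 / 30.4375 = 8.3 months

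**iPFS under each sentence.**

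| Timeline | Event sentence governs | Censoring sentence taken literally |
|---|---|---|
| iUPD wk 8, iSD wk 16, iUPD wk 24, iCPD wk 36 | Event, 5.6 months | Censored, 8.3 months |
| iUPD wk 8, iPR wk 16, iUPD wk 24, no further scan | Event, 5.6 months | Censored, 5.6 months |
| iUPD wk 8, iPR wk 16, death wk 22 | Event, 5.1 months | Censored, 3.7 months |
| iUPD wk 8, iPR wk 16, iPR wk 24, no later event | Censored, 5.6 months | Censored, 5.6 months |
| iUPD wk 8, iCPD wk 16 | Event, 1.9 months | Event, 1.9 months |

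The readings differ only where an annulled iUPD is followed by a qualifying iUPD or death. All three such timelines change from event to censored. In the death example no scan was missed (the next was due at week 24), so the rule on missing assessments does not explain the censoring.

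**iDOR.** The censoring sentence does not require the annulled iUPD to come after the response. Take iUPD at week 8, iPR at week 16, iUPD at week 24 and iCPD at week 36, counting both boundary days:

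- Event sentence: (169 − 113 + 1) / 30.4375 = 57 / 30.4375 = 1.9 months, event.
- Literal censoring: (253 − 113 + 1) / 30.4375 = 141 / 30.4375 = 4.6 months, censored.

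**Direction.** Replacing a progression by censoring at the same or a later date removes a step from the Kaplan-Meier curve and can only raise it. Replacing a death by censoring at the preceding scan can lower the curve slightly between the two dates, but raises it from the death date on.

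**How many patients.** The documents give no frequency. Let p be the assumed share of patients with the full pattern, that is, an annulled iUPD and a later qualifying event. In an arm of 20 the expected number is 20p, and the chance of at least one is 1 − (1 − p)^20.

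| p (assumed) | Expected reclassified | Chance of at least one |
|---|---|---|
| 2% | 0.4 | 33% |
| 5% | 1 | 64% |
| 10% | 2 | 88% |
| 15% | 3 | 96% |

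**The case against.** The best defence is that the censoring sentence was meant for whoever is left over: patients with no iUPD and no death, or with an iUPD that was annulled and nothing further. The event sentence comes first and includes death without exception. Section 8.2.1 keeps assessments up to the first iCPD, which would serve little purpose for these patients if an annulled iUPD ended the matter. Section 8.3.5 has no censor category for an event after an annulled iUPD. Under the literal reading such a patient would have to be labelled as having no progression or death, which would be untrue.

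This defence stands as evidence of intent. A reader might infer that the SAP has a settled rule that discards these events, and the documents do not support that. The defence does not remove the conflict, because the missing condition is in neither section and nothing ranks the two sentences.

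Three other stronger readings also fail:

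- A reader might date the event in the first timeline at week 8, as the first iUPD with any later iCPD. That treats an iUPD annulled at week 16 as confirmed, which is strained. It would also shorten iPFS.
- With 4 responders, one reclassified patient is 1/4 = 25% of responders. It is 25% of events only if all four have events.
- A percentage assumed for annulled iUPD alone gives only a ceiling, since the loss also needs a later event.

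The practical weight is limited. SAP 2 plans no efficacy hypothesis tests, and the protocol's expansion success rule uses ORR. The attached shells show iPFS and iDOR only per subject (Listing 16.2.6.2). Listing 16.4.6.2 shows every iRECIST time point, so a misclassified patient could be found. SAP 8.1 and 8.3.5 nevertheless still plan the summaries.

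**Conclusion.** The point holds as an internal conflict in SAP 8.2.5 and 8.2.6. If the censoring sentence is followed as written, later confirmed progressions and deaths in patients with an annulled iUPD become censored records, and iPFS and iDOR are biased upward. In the worked patient the result moves from an event at 5.6 months to censoring at 8.3 months. Across an arm of 20 the expected number reclassified is 0.4 to 3. This rests entirely on the assumed 2% to 15% with the full pattern and on the literal reading being the one programmed. If the event sentence is programmed instead, nothing is lost. No error rate, power or sample size figure is affected. The wording should still be corrected, because it can give a wrong result and is easy to repair.

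**What to change.** In both 8.2.5 and 8.2.6:

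1. State that an iUPD annulled by a later iSD, iPR or iCR is disregarded, and that the next qualifying iUPD (confirmed by iCPD, or not followed by iSD, iPR or iCR) or death sets the event date.
2. Limit the censoring sentence to subjects with no iUPD or death, and to subjects whose iUPDs were all annulled and who have no later qualifying iUPD, iCPD or death.
3. Make both statements subject to the handling of antineoplastic therapy in 8.2.1 and 8.3.5 and to the 8.3.5 censoring for two or more missing assessments. Without this, a rule censoring only subjects with no event would override those categories. Section 8.2.6 refers to the table on missing assessments for PFS but not for iPFS, so the cross-reference should be written out.

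The cost is a wording change and a small change to the derivation code, with no new data. iPFS and iDOR may look slightly shorter than under the literal rule.

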8.2.7. Overall Survival (OS)

Overall survival (OS) is calculated from the date of first WTX-330 dose to the date of death. The subjects without death during study will be censored at the date of last known alive.

8.3. Analysis of Efficacy Outcome Variables

8.3.1. Analysis of Target Lesion Sizes and Individual Assessments

For sum of target lesion in solid tumor, longest diameters for non-nodal lesions and short axis for nodal lesions will be added by subject and assessment visit. Assessments after the start of subsequent anticancer therapy will not be included when deriving the change from baseline (CFB) and best (i.e., the minimum of) percent CFB.

For sum of the product of the diameters in Lymphomas, the product of the diameters of each measurable lesion will be added by subject and assessment visit. Assessments after the start of subsequent anticancer therapy will not be included when deriving the change from baseline (CFB) and best (i.e., the minimum of) percent CFB.

A line (spider) plot for the percent CFB of sum of target lesion diameters over time in solid tumor and the percent CFB of sum of the product of the diameters over time in Lymphomas will be made for each subject in escalation part and expansion part.

A waterfall plot for best percent CFB of sum of target lesion diameters in solid tumor best percent CFB of sum of the product of the diameters over time in Lymphomas will be made for each subject in escalation part and expansion part. The plot is restricted to subjects with measurable disease at baseline and at least one valid post-baseline assessment.

Swimming lane plots will be presented for time (month) on treatment, iRECIST response assessments in solid tumor or Lugano response assessments in Lymphomas at all visits, as well as reasons for WTX-330 discontinuation for each subject in escalation part and expansion part.

8.3.2. Analysis of Deauville Scale

Deauville 5-point scale in FDG PET/CT include: score 1 - no uptake; score 2 - uptake < to mediastinum; score 3 - uptake > mediastinum but < liver; score 4 - moderately increased uptake > liver; score 5 – markedly increased uptake and or new lesions (s) likely to be lymphoma; score x - new areas of FDG uptake unlikely to be related to lymphoma. The shift of 5-point scale from baseline to post-baseline at each scheduled visit will be summarized.

8.3.3. Analysis of ORR and iORR

The number and percentage of subjects with BOR per RECIST 1.1, with iBOR per iRECIST, and with BOR per Lugano in each of the response categories will be summarized descriptively. ORR, iORR, and their 2-sided 95% confidence intervals being estimated with Clopper-Pearson method will be presented.

QMS Document Name: Statistical Analysis Plan Template(EN)	Page 21 of 41
QMS No (include version ref): STF-015-GL.03	Document date: 14JUL2022
CONFIDENTIAL	

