### Primary (Dose Expansion) Analysis

For primary analysis of the Dose Expansion (Part 2) cohorts, a probability of success design for the ORR based on the best overall response (BOR) will be used. To model the primary analysis of the dose expansion cohorts, 2 independent Bayesian beta binomial designs with beta (0.05, 0.95) prior distributions will be used. The response criteria for success are defined as follows: the study is considered successful in an extension arm if the posterior probability that the true response rate exceeds 10% is at least 90%. The final analysis will take place after the completion of the dose expansion cohorts when the last patient has had the final end-of-study visit.

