1.1. Changes to the Protocol Defined Statistical Analysis Plan

There is no major changes from the originally planned statistical analysis specified in the protocol v02 dated 06 April 2023, except for the addition of Efficacy Evaluable Analysis Set, Pharmacodynamics Analysis Set, and ADA analysis set.

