1.2. Study Objectives and Endpoints

Objectives	Outcome Variables
Primary Objectives and Endpoints for Dose Escalation	

 To determine the MTD and/or recommended dose for expansion (RDE). 	
 Frequency, severity, and relatedness of treatment-emergent adverse events (TEAEs) and serious adverse events (SAEs), changes in safety laboratory parameters, and DLTs (if observed) for WTX- 330.
Dose Escalation and Expansion (Parts 1 and 2)	

 To further characterize the safety of WTX- 330 	
 Frequency, severity, and relatedness of TEAEs and SAEs, changes in safety laboratory parameters, and DLTs (if observed) for WTX-330

 To evaluate the anti-tumor activity of WTX-330 	
 Overall response rate (ORR) (complete response [CR] + partial response [PR]), duration of response (DOR) by Response Evaluation Criteria in Solid Tumors (RECIST) 1.1 and immune-overall response rate (iORR) (immune-complete response [iCR] + immune-partial response [iPR]) by immune-RECIST (iRECIST), or response by Lugano criteria (for lymphoma only)
Secondary Objectives and Endpoints (Parts 1 and 2)	
	
	

 To evaluate the immunogenicity of WTX330 	
 Incidence and titers of ADAs towards WTX-330

QMS Document Name: Statistical Analysis Plan Template(EN)	Page 6 of 41
QMS No (include version ref): STF-015-GL.03	Document date: 14JUL2022
CONFIDENTIAL	

Objectives	Outcome Variables
Secondary Objectives and Endpoints (Parts 2)	

 To evaluate the antitumor activity of WTX-330 in patients with relapsed/refractory (r/r) advanced or metastatic malignancies who have progressed on CPIs or who have tumor indications for which CPIs are not approved 	
 ORR (CR + PR) based on best overall response (BOR) DOR Disease control rate at month 3, 6 and 9 Progression free survival (PFS) per RECIST v1.1 (solid tumor) and iRECIST or Lugano classification (lymphoma; Cheson et al., 2014) assessed by Investigator. Overall survival (OS)
Exploratory Objectives and Endpoints (Parts 1 and 2)	

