1.3.2. Dose Expansion

Once the MTD/RDE is identified from Dose Escalation (Part 1), the Dose Expansion part (Part 2) will open and begin enrollment. Patients will have a confirmed diagnosis of a r/r locally advanced or metastatic solid tumor or lymphoma for which the patient has progressed on or is intolerant of standard therapy, or for whom no standard therapy with proven benefit exists. Dose Expansion will be conducted in 2 arms that will enroll patients based on the following criteria:

- Arm A: Patients with indications for which a CPI is indicated/approved (e.g., cutaneous malignant melanoma, RCC, non-small cell lung cancer [NSCLC], head and neck squamous cell carcinoma [HNSCC], urothelial carcinoma, etc.) who have received a CPI regimen and who demonstrate primary or secondary resistance to CPI therapy.
- Arm B: Patients with tumor types for which CPI therapy is not indicated/approved (e.g., pancreatic cancer, microsatellite-stable [MSS] colorectal carcinoma, castrate-resistant prostate cancer (CRPC), non-Hodgkin lymphoma) and who are CPI naïve. Patients with NHL should have either follicular lymphoma or diffuse large B-cell lymphoma (DLBCL), though other subtypes of NHL such as T-cell lymphomas may be considered after discussion with the Sponsor. All patients with NHL must have received at least 2 prior systemic therapies.

2. Statistical Hypotheses

Hypothesis testing is not preplanned in this study for efficacy endpoints. Confidence intervals may be provided for information purposes only.

QMS Document Name: Statistical Analysis Plan Template(EN)	Page 8 of 41
QMS No (include version ref): STF-015-GL.03	Document date: 14JUL2022
CONFIDENTIAL	

3. Sample Size Considerations

The overall sample size for this study is approximately 75 patients between the dose escalation and dose expansion parts of the study and will depend on the observed DLT profiles of WTX-330.

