4.1. Interim Analyses

Each dose escalation step is considered an interim analysis. The BLRM will be updated with the respective number of subjects treated and the number of DLTs observed in the last cohort. The updated model will then give a statistical recommendation for the next escalation step. In addition, a risk-benefit assessment that includes a comprehensive analysis of safety and available clinical information will be done to decide on the next escalation steps.

QMS Document Name: Statistical Analysis Plan Template(EN)	Page 9 of 41
QMS No (include version ref): STF-015-GL.03	Document date: 14JUL2022
CONFIDENTIAL	

After the dose escalation an interim analysis to review the safety data may be performed for this trial. The analyses will be based on a data snapshot. As this trial is of exploratory nature and no inferential statistics are planned, no adjustment for multiple testing will be done.

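### The SAP does not carry out the protocol's primary Dose Expansion analysis: no posterior probability or success decision on ORR is planned for either arm, and the omission is not declared

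*SAP*

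**What the plan says.** **Protocol synopsis.** ORR is a primary objective of Dose Expansion (Key Study Objectives). Under Primary (Dose Expansion) Analysis, "a probability of success design for the ORR based on the best overall response (BOR) will be used", and "2 independent Bayesian beta binomial designs with beta (0.05, 0.95) prior distributions will be used". The criterion is that "the study is considered successful in an extension arm if the posterior probability that the true response rate exceeds 10% is at least 90"%. Separately, under Efficacy Analyses, the synopsis plans the ORR percentage with a 95% confidence interval.

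**SAP analysis text.** Section 8.3.3 tabulates the response categories and adds that "ORR, iORR, and their 2-sided 95% confidence intervals being estimated with Clopper-Pearson method will be presented". The overview table in Section 8.1 lists the same items. Section 2 states: "Hypothesis testing is not preplanned in this study for efficacy endpoints. Confidence intervals may be provided for information purposes only".

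**SAP sample-size text.** Section 3.2 gives a beta-binomial model with Beta(0.5, 0.5) priors and the same 10%/90% criterion, translated into at least 4 of 20 responders. Its stated purpose is to show what the chosen sample sizes can deliver. Arms may enrol up to 20 patients each.

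**SAP status of ORR.** Section 1.2 lists ORR twice. One entry is in a block headed for Parts 1 and 2 that is labelled neither primary nor secondary. The other, ORR based on BOR, is under the Part 2 secondary endpoints.

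**SAP declared changes.** Section 1.1 says "There is no major changes from the originally planned statistical analysis specified in the protocol v02 dated 06 April 2023", apart from three added analysis sets.

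**The concern.** A primary analysis named in the protocol should reappear in the SAP as an instruction: model, prior, analysis set, denominator and decision. Here it appears only as design background. A programmer working from Sections 8.1 and 8.3.3 would deliver counts, percentages and exact intervals, and would have no reason to compute a posterior.

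Two things are at stake. The clinical study report could lack the protocol's primary expansion result without anyone having decided to drop it. And if someone later asks whether an arm succeeded, the prior and the denominator would be chosen with the response counts already known. The two documents offer two priors, and at n = 20 they disagree for exactly one outcome, 4 responders.

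**Working it through.** **Inputs.** Protocol prior Beta(0.05, 0.95); SAP 3.2 prior Beta(0.5, 0.5); reference rate 10% and threshold 90% (both documents); n up to 20 per arm (SAP 3.2).

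**Formulas.** With x responders among n and prior Beta(a, b), the posterior is Beta(a + x, b + n − x). So P(ORR > 10%) = 1 − F(0.10; a + x, b + n − x), where F is the beta distribution function. The chance of success at true rate p is P(X ≥ c), with X binomial(n, p) and c the smallest successful count.

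**Step 1: reproduce the SAP table.** With n = 20 and c = 4, P(X ≥ 4) at true ORR 10, 15, 20, 25, 30, 40, 50 and 60% is 13.3, 35.2, 58.9, 77.5, 89.3, 98.4, 99.9 and 100%. All eight figures match SAP 3.2.

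**Step 2: apply the rule at n = 20.**

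| Responders | Beta(0.5, 0.5) | Beta(0.05, 0.95) | Clopper-Pearson 95% CI |
|---|---|---|---|
| 3 | 0.786 | 0.689 | 3.2–37.9% |
| 4 | 0.922 | 0.874 | 5.7–43.7% |
| 5 | 0.977 | 0.959 | 8.7–49.1% |

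The cut-off is 4/20 under the SAP prior and 5/20 under the protocol prior.

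**Step 3: operating characteristics of each cut-off (n = 20).**

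| True ORR | 10% | 15% | 20% | 25% | 30% | 40% |
|---|---|---|---|---|---|---|
| P(X ≥ 4) | 13.3% | 35.2% | 58.9% | 77.5% | 89.3% | 98.4% |
| P(X ≥ 5) | 4.3% | 17.0% | 37.0% | 58.5% | 76.3% | 94.9% |

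At a true ORR of 20%, the decision depends on the prior with probability 0.5886 − 0.3704 = 0.218, the chance of exactly 4 responders.

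**Step 4: let n vary within the plan.** The smallest successful count, for n from 10 (an illustrative lower end) to 20, is:

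- Beta(0.5, 0.5): 3 for n = 10–14, 4 for n = 15–20.
- Beta(0.05, 0.95): 3 for n = 10–11, 4 for n = 12–18, 5 for n = 19–20.

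A fixed 4/20 is therefore not a complete statement of the rule when arms may be smaller than 20.

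**Step 5: look for the posterior elsewhere in the SAP.**

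| Place | Content |
|---|---|
| 3.2 | Model and rule, as sample-size illustration |
| 4.2 | One final primary analysis announced; no method named |
| 8.1, 8.3.3 | Response categories, ORR, Clopper-Pearson CI |
| Shells 14.2.1.2.1 and 14.2.1.2.2 | BOR, ORR, exact CI, clinical benefit rate; Arm B solid tumors only |
| 1.1 | Only added analysis sets declared |

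No section or shell computes P(ORR > 10%) or records a success decision.

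**The case against.** **The rule is already in SAP 3.2, and the result can be recovered.** Partly right. For Arm A, the responder count and N in Table 14.2.1.2.1 are enough for anyone to compute the posterior once a prior is fixed. So a reader who infers that the information is lost goes too far; the result is unplanned and unreported, but not destroyed. What stands is that Section 3.2 gives no analysis instruction and uses a prior other than the protocol's. For Arm B, the shell's solid-tumor denominator is not the whole arm.

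**ORR has been demoted to secondary.** A reader might infer this from the Part 2 secondary list, but the documents do not support it in that form. ORR also stands in the unlabelled block ahead of the secondary headings, and SAP 8.2.3 defines ORR through BOR anyway. Its status is unclear; it has not plainly been downgraded.

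**The confidence interval has replaced the rule or contradicts it.** Also tempting, since the intervals at 4/20 and 5/20 both cover 10%. But the protocol itself plans both the rule and a 95% interval, and no document uses the interval's lower limit as a decision criterion. Section 8.3.3 correctly carries out the protocol's descriptive item; the fault is that it stops there.

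**The trial is exploratory.** Section 4.1 says "As this trial is of exploratory nature and no inferential statistics are planned", but it does so while explaining why interim looks carry no multiplicity adjustment. Sections 2 and 13 exclude hypothesis testing, and a posterior threshold need not be a hypothesis test. These sentences neither cancel the protocol's criterion nor declare its removal.

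**The shells are a selection.** True: their modification history records that outputs were selected for an aCSR, and they omit the Kaplan-Meier and waterfall plots planned in Section 8.3. The finding therefore rests on Sections 8.1 and 8.3.3. Likewise, under the SAP prior the cut-off is 4 for every n from 15 to 20, and Appendix 6 replaces many patients without a post-baseline assessment, so the varying-n point bites mainly under the protocol prior or in a small arm.

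**Conclusion.** The concern holds. The protocol's primary expansion analysis has no counterpart in the SAP's analysis sections, and Section 1.1 does not declare its absence. It should be corrected before the final analysis, because the SAP as written yields no primary expansion decision for Arm A or Arm B.

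The posterior figures above do not measure harm from the omission alone. They show why the calculation must be specified in advance rather than rebuilt afterwards. The prior conflict is a distinct defect, but it has to be settled for the missing analysis to be added; settling it would not by itself put a posterior into the SAP.

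Assumptions: only the synopsis of the protocol is available here, so fuller statistical text in its body, if any, could not be checked; the n = 20 figures take a full arm as analysed.

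**What to change.** - **SAP 8.3.3 and the expansion response table:** for each arm, add responders over n analysed, P(ORR > 10% given the data) computed on the actual n, and success yes/no.
- **Prior:** name one and use it in both documents. Keeping Beta(0.05, 0.95) means restating SAP 3.2 with cut-off 5/20 and the second row of the Step 3 table, with no protocol amendment. Adopting Beta(0.5, 0.5), cut-off 4/20, changes the protocol's primary analysis text and so needs an amendment.
- **Arm B:** add a whole-arm row combining the RECIST and Lugano responses, since the current shell leaves lymphoma patients out.
- **SAP 1.2:** label Part 2 ORR by BOR as primary and remove the duplicate listing.
- **Clopper-Pearson interval:** keep it as the descriptive summary the protocol also plans.
- **If the sponsor intends to drop the rule:** say so, with the reason, in SAP 1.1.
- **Optional:** clarify in Sections 2, 4.1 and 13 that the absence of hypothesis tests does not remove the Bayesian decision rule.

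The cost is a few lines of SAP text and a few table rows, plus the Arm B row. No extra patients or data are needed, and each posterior is one evaluation of the beta distribution function.
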